#### Other End-points

- Safety and tolerability
  - Tissue responses as assessed by gross pathology and histology will be described
  - Adverse Effects profile will be monitored
- Seed integrity post excision;
- Number of days the marker (seed) was in place;
- Mastectomy weight
- Relationship between clinical characteristics and movement of the markers -- If any markers migrate a clinically significant distance, a qualitative assessment will be carried out to see if there is a possible relationship between clinical characteristics seen in patients and movement of the marker. (e.g. Haematoma, placement of seed into fatty rather than soft tissue)

**Type of trial:** Single site, single arm, open label safety and feasibility cohort study of using magnetic marker seeds to localise breast tumours.

**Trial design and methods:** The magnetic marker system (Sentimark® Magnetic Marker System) is a sterile, single use device composed of a magnetic marker (seed) preloaded in a delivery system. The magnetic seed is approximately 5mm long and 0.9mm in diameter.

The seed is intended to be temporarily placed within the breast and removed within 28 days. The seed, when used in conjunction with the Sentimag® System (base unit and probe), can be used as a guide for the surgeon to facilitate excision of tissue. The Tissue

Marker (seed) is visible using ultrasound and mammography.

The study is a first-in-human study using this particular magnetic seed and designed to test the feasibility and safety of using the marker (seed) in breast cancer patients. The data will support the application for a CE mark.

The study will be carried out in patients requiring a mastectomy. In this population, the full cycle of marker (seed) deployment and removal can be evaluated, but as the breast is being removed as part of the planned cancer treatment, patient treatment will be unaffected should the magnetic seed not perform as intended.

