## **5.6 Withdrawal of Subjects**

Safety of the study participants will be monitored by the Chief Investigator. It is unlikely there will be Serious Adverse Events directly related to the Sentimark as it is similar to devices currently in use to mark breast cancer location. The study involves an intervention of Sentimark placement within the breast. Patients may withdraw consent to have this procedure performed in which case this will be recorded and the patient will be withdrawn from the study and will be replaced by another subject. If a patient withdraws consent to the study once the Sentimark has been placed, they will be withdrawn from the study but information on the cancer

excision surgery will be recorded to ensure the Sentimark magnetic marker (seed) was removed as part of the breast cancer surgery.

Each participant has the right to withdraw study at any time. In addition, the investigator may discontinue a participant from the study at any time if the investigator considers it necessary for any reason including:

- Ineligibility (either arising during the study or retrospective having been overlooked at screening);
- Significant protocol deviation;
- Significant non-compliance with treatment regimen or study requirements;
- An adverse event which requires discontinuation of the study medication or results in inability to continue to comply with study procedures;
- Disease progression which requires discontinuation of the study medication or results in inability to continue to comply with study procedures;
- Consent withdrawn;
- Lost to follow up.

It is understood by all concerned that an excessive rate of withdrawals can render the study un-interpretable; therefore, unnecessary withdrawal of patients should be avoided. Should a patient decide to withdraw from the study, all efforts will be made to report the reason for withdrawal as thoroughly as possible.

Withdrawal from the study will result in exclusion of the data for that participant from analysis.

The reason for withdrawal will be recorded in the CRF.

If the participant is withdrawn due to an adverse event, the investigator will arrange for follow-up visits or telephone calls until the adverse event has resolved or stabilised.

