### 9.2.3 Reporting Form

The reporting form template for the summary SAE tabulation is given in the Appendix of this document.

The table gives a cumulative overview of the reportable events per clinical investigation and will be updated and transmitted to participating NCAs each time a new reportable event or a new finding to an already reported event is to be reported. More detailed information has to be provided on request of an NCA, if so requested by using the individual reporting form. The sponsor shall identify the new/updated information in the status column of the tabular form featured in the Appendix as:

a = added = new reportable event;

m = modified = new finding/update to an already reported event;

u = unchanged.

Changes in a line should be highlighted in bold and/or colour in the respective column.

The reporting form is study specific and covers only a given clinical investigation, defined by a distinct clinical investigation plan. English is the recommended language for the reporting form. The report should be sent by email in Excel to the participating NCAs, or an equivalent format which allows using the inserted filters. The reporting to MHRA shall use the form template for the summary SAE tabulation as given in the Appendix of MEDDEV 2.7.3 December 2010.

Safety Oversight:

The Trial Steering Committee will meet once all patients have completed the study or earlier if considered necessary by the Chief Investigator. They will consider all Serious adverse events and adverse events and the main safety and efficacy outcomes. Notably they will discuss:

Morbidity and safety of seed placement – recording of any morbidity as a result of Study visit 1 or 2;

Detectability of the seed in the breast. – measured at Study visits 1 and 2 using the hand-held magnetometer;

Assessment of migration of the seed from time of deployment to time of surgery.

Measured on difference in position of magnetic marker (seed) from the cancer

between Study Visits 1 and 2, and assessed on mammograms by a Consultant Radiologist.

If any markers migrate a clinically significant distance, a qualitative assessment will be carried out to see if there is a possible relationship between clinical characteristics seen in patients and movement of the marker. (e.g. Haematoma, placement of seed into fatty rather than soft tissue)

Adverse tissue responses as assessed by gross pathology and histopathology.

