### **10. Statistics**

#### **10.1 Sample Size**

This protocol has been developed with [name] Medical Statistician at Manchester University.

The sample size has been set at 25 patients to achieve a balance between having sufficient numbers to observe any unexpected patterns of seed migration and keeping to a minimum the number of patients exposed to any risk through participating in the study as no direct benefit is to be expected for participants who consent to taking part in the trial.

RSL seeds are a product similar in size and shape to Sentimark, in widespread clinical use in the same indication, and considered to be safe and effective. In the literature Alderliestenxiii, et al. [2011] report a mean migration of 0.8mm, range 0 to 2.8mm (N=10) for RSL seeds which was considered “clinically negligible” by the authors.

Migration of Sentimark in preclinical studies where the seed is deployed in soft mammary tissue showed a mean migration of 0.95mm, range 0 to 3.6mm (N=10) and no abnormal tissue reaction. Migration observed is substantially similar to that reported by Alderliesten et al for RSL seeds.

From the experience with RSLs, clinically significant migration of radioseeds (greater than 1cm) in larger studies has been reported in 3/456 placements (Grayxiv et al [2004], Sungxv et al [2013]). However when it does occur the reason is often either a pre-existing or newly formed haematoma or placement of the seed into fatty rather than soft tissue.

For this reason, clinical characteristics of patients in whom a seed migrates more than 1cm will be carefully evaluated.

Formally, the 95% CI if 0 out of 25 seeds migrate >10mm is 0-13%. However, findings will be considered in conjunction with other observations including:

- The observed distribution of migration (e.g. how variable is this distribution and how close does it lie to the limits)
- For any seeds migrating >10mm, a qualitative assessment of underlying characteristics such as haematoma or placement into fatty tissue (both reported as causes of migration in RSL procedures)
- Abnormal tissue responses will be assessed by gross pathology and histology, as part of the safety endpoint.

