## **10.3 Analysis**

Simple descriptive summary statistics of the main parameters will be derived together with a graphical presentation of the raw data. Percentages for categorical variables, means, standard deviations, medians and range values for quantitative factors will be calculated as appropriate. 95% confidence intervals will also be presented to provide a measure of accuracy for the estimates.

The relationship between breast size and detectability of the seed by the magnetometer will be assessed using simple correlational analysis.

The statistical software package, SPSS version 22, will be used for the statistical analysis.

Sources of measurement error will be graphically displayed, reviewed and discussed as appropriate.

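### A patient who stops the placement after the needle is introduced but before a seed is deployed is withdrawn, replaced and left out of the analysis, and no result is reported per attempted placement

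*Combined protocol and SAP*

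**What the plan says.** Section 5.6 (Withdrawal of Subjects) has two consent branches.

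- **Consent to the placement procedure is withdrawn.** "Patients may withdraw consent to have this procedure performed in which case this will be recorded and the patient will be withdrawn from the study". The sentence ends by saying that another subject replaces her.
- **Consent is withdrawn once the seed is in the breast.** The patient is withdrawn, removal of the seed at surgery is still recorded, and no replacement is mentioned.

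The section then states that the data of any withdrawn participant are excluded from analysis, and that the reason for withdrawal goes in the CRF. It also lets the investigator discontinue a participant for any reason. The examples listed there do not include a failed placement.

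Elsewhere, the Summary (section 1) describes the study as "designed to test the feasibility and safety of using the marker (seed) in breast cancer patients" and says of women having mastectomy: "In this population, the full cycle of marker (seed) deployment and removal can be evaluated". Under Safety Oversight in section 9.2.3, the Trial Steering Committee is to discuss "Morbidity and safety of seed placement – recording of any morbidity as a result of Study visit 1 or 2". The Methods part of the Summary has adverse events recorded from signed consent onwards. Section 10.1 states: "The sample size has been set at 25 patients to achieve a balance".

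**The concern.** The dividing line in 5.6 is whether a seed has been placed. It is not whether placement was attempted. A patient who stops the procedure with the needle already in (because of pain or bleeding, for example) has no seed, so she falls in the first branch with the patient who changed her mind at home. Both are withdrawn, replaced and excluded.

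Replacing the patient who declined beforehand does no harm, because she carries no device information. The patient who stopped part-way has been exposed to the delivery procedure. Her experience is evidence on tolerability and feasibility of placement, and any injury is placement morbidity, which the committee is asked to judge. Section 9.1 lists haematoma after placement among the events to be reported, and section 10.1 names haematoma as a cause of seed migration. An attempt stopped for bleeding is therefore relevant to what the study wants to learn, and section 13 says the results will support a CE marking application.

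**Working it through.** **1. The plan's own figure.** Section 10.1 states: "Formally, the 95% CI if 0 out of 25 seeds migrate >10mm is 0-13" (per cent). For 0 events in n = 25:

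- Wilson upper limit = z²/(n + z²) = 3.8415/28.8415 = 13.3%.
- Exact (Clopper-Pearson) two-sided upper limit = 1 − 0.025^(1/25) = 13.7%.

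The stated 13% is reproduced by Wilson and lies within one percentage point of the exact limit. An unplaced seed has no migration value, and the patient is replaced, so the rule in 5.6 does not alter this figure.

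**2. Where a patient who stops part-way ends up.**

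| Situation | Handling in 5.6 | Data analysed? |
|---|---|---|
| Withdraws consent before any attempt | Withdrawn, replaced | No; nothing is lost on the device |
| Withdraws consent after the needle is introduced, no seed deployed | Same branch: withdrawn, replaced | No; attempt and morbidity data are lost |
| Withdraws consent after the seed is placed | Withdrawn, removal recorded, no replacement stated | No |
| Technical failure, or operator abandons the attempt, consent intact | No stated handling | Not stated; excluded if the investigator uses the open discontinuation clause |

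**3. Does any other section bring her back?** The endpoints in 4.1.1 and 7.2 are migration, distance from the intended site, percentage within the target area, and detectability against depth. Each needs a seed in the breast. Section 10.3 promises that "95% confidence intervals will also be presented to provide a measure of accuracy for the estimates", but it defines no analysis set and no rate per attempt. The schedule in section 6 marks adverse event review at Visits 2 and 3, not at Visit 1, where placement occurs. The Summary's wider rule does collect events from consent, but the exclusion in 5.6 still takes them out of the analysis.

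**4. Size, under assumed counts.** The documents give no rate of unsuccessful or stopped attempts. Let k be the number of attempts that end without a seed while 25 seeds are placed. Placement success is 25/(25 + k), with Clopper-Pearson limits: the lower is the 2.5% point of Beta(25, k + 1), and the upper is the 97.5% point of Beta(26, k), or 100% when k = 0.

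| k (assumed) | Success per attempt | Exact 95% CI |
|---|---|---|
| 0 | 25/25 = 100% | 86.3% to 100% |
| 1 | 25/26 = 96.2% | 80.4% to 99.9% |
| 2 | 25/27 = 92.6% | 75.7% to 99.1% |
| 3 | 25/28 = 89.3% | 71.8% to 97.7% |

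**5. How likely is k ≥ 1?** If each attempt has probability p of ending without a seed, the chance of at least one such event in 25 attempts is 1 − (1 − p)^25. This gives 40% at p = 2%, 72% at 5% and 93% at 10%. The number expected before 25 seeds are placed is 25p/(1 − p), which is 0.5, 1.3 and 2.8. These values of p are assumptions and cover every cause. The written replacement rule reaches only the attempts that the patient herself stops.

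**The case against.** The strongest reply is that the sentence in 5.6 is about consent and nothing else. A reader might infer that every failed or abandoned placement is replaced, that recruitment runs until 25 placements succeed, and that placement success is therefore 100% by construction. The documents do not support any of these. A consenting patient whose lesion cannot be reached, or whose device fails to deploy, is not withdrawn or replaced under any written rule. The plan is silent on her. That part of the objection stands in full.

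Three further replies stand in part.

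- **Replacement deletes nothing.** Replacement only adds a subject. The separate exclusion sentence removes the data, so it must be amended too. Amending it alone would still leave no attempt denominator.
- **Placement problems are not invisible.** The withdrawal and its reason are recorded, adverse events are collected from consent, section 9.1 defines device deficiency to include malfunction and use error, and the committee considers all adverse events. A count could therefore be compiled. The plan does not commit to reporting one, and its exclusion rule points the other way.
- **No deployment success rate is promised.** The full-cycle sentence explains the choice of mastectomy patients, and conditioning on a placed seed is inherent in a migration endpoint. This is true, and it is why the migration result is not in question. It does not justify dropping exposed patients from the safety and feasibility summaries.

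**Conclusion.** The point holds in a limited form. A stated rule withdraws, replaces and excludes from analysis a patient who withdraws consent during placement, after the needle is introduced and before a seed is deployed. No planned result has attempted placements as its denominator. Technical failures and attempts abandoned by the operator have no stated handling, and the open-ended discontinuation clause could bring them under the same exclusion.

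This rests on reading a withdrawal part-way through as a withdrawal of consent to the procedure. That is the natural reading, because the only other consent branch begins once the seed is in place.

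The primary migration interval does not change. The effect is confined to safety and feasibility reporting. Its size is unknown because no rate is given. With one to three attempts uncounted, a figure that would read 25/25 is in fact 96% to 89%, and the exact lower limit moves from 86% to between 80% and 72%. These figures illustrate assumed counts. They are not predictions, and the plan does not itself propose to report 25/25.

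**What to change.** **Section 5.6.** Limit replacement with exclusion of data to patients who withdraw before the delivery needle is introduced. Amend the exclusion sentence so that data collected up to withdrawal from any patient with an attempted placement are kept, as far as her consent allows, in a placement-attempted set. State that technical failures and attempts abandoned by the operator belong to this set.

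**Section 10.3.** On that set, report seeds placed over attempts with an exact 95% CI, together with placement-related adverse events and device deficiencies. Keep the migration endpoint on placed seeds, with replacement allowed so that it still reaches 25.

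**Cost.** A few sentences in 5.6 and 10.3 and one CRF item (needle introduced, seed deployed, reason if not). Because these additions are small, the main price is that the reported feasibility figure may be slightly less favourable.

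### Dropping every withdrawn participant's data can remove migration and adverse-event cases after the seed is placed, biasing the primary and safety results towards no problem

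*Combined protocol and SAP*

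**What the plan says.** Section 5.6 (Withdrawal of Subjects) sets the rule: "Withdrawal from the study will result in exclusion of the data for that participant from analysis". It also lets the investigator discontinue a participant at any time, for any reason thought necessary. The listed reasons include:

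- "An adverse event which requires discontinuation of the study medication or results in inability to continue to comply with study procedures"
- "Ineligibility (either arising during the study or retrospective having been overlooked at screening"
- "Significant protocol deviation", with no definition of significant
- loss to follow-up.

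The section foresees withdrawal after placement: "If a patient withdraws consent to the study once the Sentimark has been placed, they will be withdrawn from the study". In that case only information on the excision surgery is kept, to confirm that the seed came out. Replacement is stated only for patients who withdraw consent to the placement procedure.

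Section 10.3 (Analysis) plans descriptive statistics with 95% confidence intervals. It defines no analysis population, safety set or missing-data rule. Section 10.1 (Sample Size) gives the precision: "Formally, the 95% CI if 0 out of 25 seeds migrate >10mm is 0-13" percent. On the causes of migration in radioactive-seed practice it says: "However when it does occur the reason is often either a pre-existing or newly formed haematoma", or else placement into fatty tissue.

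**The concern.** Several of the withdrawal reasons can depend on the outcome. An existing haematoma near the lesion is an exclusion criterion (section 5.3), and section 10.1 names haematoma as a frequent reason for migration. Section 9.1 lists both haematoma and migration beyond 10 mm among the adverse events to be reported. A patient withdrawn in connection with either would leave the migration distribution, the detection results and the tabulated adverse-event profile together.

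The primary result is a count of rare events out of 25, so losing one such patient can turn one migration into none. The results also support the CE marking application (section 13). In addition, the precision statement needs 25 evaluable seeds, and no replacement is stated once a seed has been placed.

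**Working it through.** **Inputs.** Sample size 25 and the 0 to 13% interval (section 10.1); thresholds of 10 mm and 40 mm (section 4.1.1); reference rate for radioactive seeds 3/456 = 0.66% (section 10.1). The documents give no withdrawal rate, so every withdrawal count or fraction below is an assumption.

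**1. The plan's own figure.** The interval method is not named. For 0 of n:

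- Wilson upper limit = z²/(n + z²) = 3.84/(25 + 3.84) = 13.3%, which matches the stated 13%.
- Exact (Clopper-Pearson) upper limit = 1 − 0.025^(1/25) = 13.7%, which would round to 14%.

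The stated figure therefore reproduces with Wilson. Both methods are shown below; the choice does not affect the point.

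**2. Migrators kept or dropped.** Exact limits are beta quantiles: lower B(0.025; x, n−x+1), upper B(0.975; x+1, n−x).

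| Situation | Observed | Exact 95% CI | Wilson 95% CI |
|---|---|---|---|
| One migrator, kept | 1/25 = 4.0% | 0.1 to 20.4% | 0.7 to 19.5% |
| Same patient withdrawn | 0/24 = 0% | 0 to 14.2% | 0 to 13.8% |
| Two migrators, kept | 2/25 = 8.0% | 1.0 to 26.0% | 2.2 to 25.0% |
| Both withdrawn | 0/23 = 0% | 0 to 14.8% | 0 to 14.3% |

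Losing one migrator lowers the exact upper limit by 20.4 − 14.2 = 6.2 percentage points and changes the finding from migration seen to none seen.

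**3. Withdrawals unrelated to outcome, no migrations.** The exact upper limit goes from 13.7% (n = 25) to 14.2% (24), 14.8% (23) and 16.8% (20). This costs precision without causing bias.

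**4. Partly selective withdrawal.** Let p be the true risk and w the chance that a migrator is withdrawn. Assume no non-migrator withdraws and 25 patients are analysed. The expected observed rate is r = p(1−w)/[p(1−w) + (1−p)], and the chance of reporting zero events is (1−r)^25. With w = 0.5:

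| True risk p | Observed rate r | P(zero events), no exclusion | P(zero events), w = 0.5 |
|---|---|---|---|
| 3/456 = 0.66% | 0.33% | 85% | 92% |
| 4% | 2.0% | 36% | 60% |
| 8% | 4.2% | 12% | 35% |

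For example, at p = 8%: r = 0.04/(0.04 + 0.92) = 4.2%. The chance of zero events is 0.92^25 = 12% without exclusion and (1 − 0.0417)^25 = 35% with it.

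**5. How a case could be lost.**

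- *Retrospective ineligibility.* A seed migrating more than 10 mm triggers a qualitative review that looks for haematoma (sections 7.1 and 10.1). If that review finds a haematoma that was already present, section 5.3 makes the patient ineligible, section 5.6 allows withdrawal, and the data go. No bad faith is needed.
- *Loss to follow-up.* Migration is measured at Visit 2, or the day before surgery. Visit 3 is 2 to 3 weeks after surgery (sections 4.2 and 5.7). A patient with a complete primary measurement who misses Visit 3 can lose all her data.

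**The case against.** The strongest case on the other side has four parts.

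- **The adverse-event reason is narrow.** It requires stopping a study medication, which this trial does not have, or being unable to continue the procedures. A haematoma does not in itself prevent the check mammogram, the detectability check or the planned mastectomy.
- **The protocol intends to study these cases.** Sections 4.1.1, 7.1, 9.2.3, 10.1 and 11 call for a qualitative assessment of any seed that migrates a clinically significant distance.
- **Oversight is preserved.** Adverse events are recorded from consent to the final visit (section 1). Adverse-event withdrawals are followed until resolved or stable (section 5.6). Migration beyond 10 mm, haematoma and unresected seeds must be reported (section 9.1). The steering committee considers all adverse events (section 9.2.3).
- **The size is hypothetical.** No withdrawal rate is given, section 5.6 discourages unnecessary withdrawal, and the study is descriptive with no pass mark. A patient is also unlikely to withdraw because of a migration not yet measured.

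Part of this stands. The bias is possible and not certain. For the primary endpoint, investigator withdrawal after measurement is a more realistic route than a patient leaving because of a placement haematoma. The safety gap concerns the analysed results and not the reporting of events. But the general discretion to withdraw for any reason overtakes the narrow adverse-event wording, and none of the safeguards says that a withdrawn participant's data return to the primary or safety analysis. The stated intent to examine migrators makes the exclusion sentence harder to defend.

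**Conclusion.** The concern holds, and the rule is wrong as written. Followed literally, it can remove the rare event the study exists to count. One excluded migrator changes the reported result from 4.0% with an exact upper limit of 20.4% to 0% with an upper limit of 14.2%.

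The direction of the bias rests on withdrawal being related to migration or harm. The size rests on assumed withdrawal numbers. At the cited radioactive-seed rate the effect is small, but the rate for this device in humans is what the study has to establish. Separately, the 0 to 13% precision is not protected against withdrawals after placement.

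**What to change.** Replace the exclusion sentence in section 5.6 with text to this effect:

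> Every participant in whom a seed was placed is included in the safety, placement, detection and migration analyses, whatever the reason for withdrawal, using all data collected up to withdrawal and the record of seed removal. Only participants withdrawn before placement are excluded and replaced. Data are left out only where a participant explicitly withdraws permission for their use.

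Add to section 10.3:

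- this analysis set by name, with a listing of withdrawals, their timing and reasons;
- a count of placed seeds with no pre-operative distance, whether not imaged or not visible;
- a sensitivity analysis counting those seeds as 10 mm or greater. Each one adds 1/25 = 4 percentage points, so it should be presented as a worst case beside the observed result.

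The cost is one paragraph in section 5.6 and a short addition to section 10.3, with no extra patients or procedures. Some included patients will have incomplete data. The wording on data use after withdrawal should be checked against what participants are told at consent, which could add a small change there.
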